The investigator, or a person designated by the investigator will collect the patient's data using the case report forms (CRF) authorized by Amgen Korea. The patient's information needed for analysis and reporting will be entered/transmitted into the validated database or data system. Study data management will be performed according to applicable standards and data cleaning procedures. The database will be locked once the quality control procedures are completed. The original CRFs will be retained by Amgen Korea. The final data collection for each patient will be performed at the time point of 24 weeks (6 cycles) or drop-out. Most of major severe AE should be detected within 6 cycles based on ASPIRE study.

- Summary of patient eligibility criteria

Inclusion criteria: A patient can be included into the study only if all of the following criteria are met:

1. Signed and dated informed consent
2. Patients diagnosed with multiple myeloma who have received at least one prior therapy
3. Patients who are prescribed with Kyprolis® (in combination with lenalidomide and dexamethasone or in combination with dexamethasone) for the first time

Exclusion criteria: All contraindications specified in the local product information have to be considered. In addition, patients treated with any regimens not specified in the approved prescribing information of Kyprolis® in Korea should be excluded from the study.

- Follow-up

- The total follow-up period is 24 weeks.
  - Safety assessment will be performed at 4 weeks, 8 weeks, 12 weeks and 24 weeks.
  - Response assessment will be performed at 12 weeks and 24 weeks.
- The study protocol does not define exact referral dates for follow-up visits. Follow-up visits occur during routine practice. The investigator documents the date of initial visit and follow-up in the case report form and follows the study procedures (usually pertaining to data collection only) for the visit.

Approved

- Variables
  - *Outcome Variables*
    - Patient demographics and medical history
    - Diagnostic information
    - Prior and Concomitant medication
    - Prior anti myeloma therapy
    - Myeloma characteristics eg, cytogenetic risk
    - Safety: Adverse events (AEs) including serious adverse events and adverse drug reactions (ADRs)
    - Effectiveness: Overall response rate (ORR, %) according to the International Myeloma Working Group (IMWG) uniform response criteria to assess the tumor response (sCR, CR, VGPR, or PR) ([Appendix F](#))

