#### 9.2.6 Study Follow-up

Each patient is followed-up at monthly visits for the first three months and then a follow-up visit at 6 months. Only safety data is collected during the first two monthly follow-up visits.

The end of follow-up for each patient is defined as death, loss to follow-up (eg, patients transferring to another clinic), 28 days from the last injection of Kyprolis® or 24 weeks after initial prescription of Kyprolis®, whichever occurs first.

\* For the combination regimen with lenalidomide and dexamethasone, administer Kyprolis® intravenously as a 10-minute infusion on two consecutive days, each week for three weeks followed by a 12-day rest period as shown in [Table 1](#). Each 28-day period is considered one treatment cycle.

For the combination regimen with dexamethasone, administer Kyprolis® intravenously as a 30-minute infusion on two consecutive days, each week for three weeks followed by a 12-day rest period as shown in [Table 2](#). Each 28-day period is considered one treatment cycle.

Approved

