**Table 3. Overview of variables collected during the study**

Schedule Procedure	Initial visit	Follow-up visits (week)			Last visit 
	Kyprolis® treatment starting	4	8	12	Final assessment (at 24 weeks) or last follow-up (28 days after last injection)
Eligibility	X				
Informed consent	X				
Demographic data 	X				
Myeloma history					
Previous medical history and Concomitant disease 	X				
Diagnostic information about multiple myeloma 	X				
Visit date	X	X	X	X	X
Treatment of Kyprolis 	X	X	X	X	X
Adverse Events 		X	X	X	X
ECOG PS	X			X	X
Tumor response assessment 				X	X

1. Site name / Investigator's name, Patient's identifier / Patient's initials, Gender / Age, Height / Weight, Pregnancy
2. Date of diagnosis, international staging system (ISS) stage at study entry, site of metastasis and previous treatment regimen for multiple myeloma or number of previous treatment
3. Please refer to the detailed dose and administration schedule in [Table 1](#) and [Table 2](#).
4. AEs tracking up to 28 days after the last injection of Kyprolis® or 24 weeks after initial prescription of Kyprolis®.
5. Evaluated according to IMWG criteria. Based on the investigator's clinical assessment if a patient could not have radiological examination, , because of deterioration of medical condition
6. The last visit will occur at 28 days after the termination of treatment or the final assessment at 24W.

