### 9.3.2 Outcome Assessment

Adverse events (including seriousness and causal relations to drug), and other safety information (eg, overdose, lack of effectiveness, pregnancy and lactation with or without adverse event) are collected as they become available throughout the follow-up period by using CRF and applicable safety reporting form.

Laboratory values measured as a part of routine medical practice are collected in CRF for baseline, 4W (ranged; 3-5W), 8W (7-9W), 12W (11-13W), and 24W (23-25W) or at the end of follow-up.

Overall response rate: The following assessments will be required for all response categories (sCR, CR, VGPR, or PR; see definitions in [Appendix F](#)– IMWG criteria): Patients with confirmed sCR, CR, VGPR, or PR will be considered to have achieved an overall response.

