### 9.3.3 Covariate Assessment

Data on the following covariates are collected in CRF.

Patient demographics and medical history: sex, birth Year/Month, height, weight, pregnancy, site name, investigator's name, medical history of disease (all cancers, and other diseases without relation with cancer within the last 2 years), cardiovascular disease, hepatic impairment, renal impairment, other concomitant diseases

Diagnostic information: information pertaining to Kyprolis® indication including date of diagnosis, international staging system (ISS) stage at study entry, site of metastasis, previous treatment for multiple myeloma or number of previous treatment and cytogenetic risk

Prior and Concomitant medication: Prior (at least 30 days) or concomitant medications including any prescription or over-the-counter preparation and targeted disease therapies or surgical treatments after start of Kyprolis® treatment. All the following variables are to be collected for concomitant medication: trade name or INN, start date (at least year), stop date or “continued” and daily dose (if applicable).

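### For patients who stop Kyprolis early, the last response reading falls 28 days after the final injection, and the protocol neither separates readings taken after a new regimen has begun nor collects the dates needed to do so

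*Protocol*

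**What the plan says.** The Abstract states the response schedule: "Response assessment will be performed at 12 weeks and 24 weeks". Table 3 marks tumor response at week 12 and in the last-visit column, and note 6 fixes that visit: "The last visit will occur at 28 days after the termination of treatment or the final assessment at 24W". Section 9.2.6 adds that the first two monthly visits collect safety data only. It ends follow-up at death, loss to follow-up, or "28 days from the last injection of Kyprolis® or 24 weeks after initial prescription of Kyprolis®, whichever occurs first". The start of another anti-myeloma therapy is not among these events.

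Sections 9.3.2 and 9.7.2.5 define the endpoint: "Patients with confirmed sCR, CR, VGPR, or PR will be considered to have achieved an overall response". Neither attaches a condition about later therapy. Section 9.7.2.1 admits to the Efficacy population any Safety-population patient treated per protocol who has any post-baseline efficacy evaluation.

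Later treatment is foreseen. Section 9.3.3 collects "targeted disease therapies or surgical treatments after start of Kyprolis® treatment", but for concomitant medication the year is the stated minimum for the start date.

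**The concern.** The secondary objective is the effectiveness of Kyprolis, measured by ORR. In routine practice a patient who stops for progression or toxicity may be on a replacement regimen within four weeks. If the response is read after that switch, it may reflect the new regimen. In the other direction, a patient who responded on Kyprolis, stopped before week 12 and lost the response before the last visit has no scheduled on-treatment reading to show it.

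Both errors arise only in early stoppers. Section 9.7.2.6.1 plans effectiveness by regimen (KRd and Kd) and by other subgroups, so those displays would be affected unequally if early stopping or switching differed between the groups.

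**Working it through.** **Inputs from the protocol.** Injections fall on days 1, 2, 8, 9, 15 and 16 of a 28-day cycle (Study Design Schema, Tables 1 and 2), "each week for three weeks followed by a 12-day rest period" (section 9.2.6). Final data collection is "at the time point of 24 weeks (6 cycles) or drop-out" (Abstract). The last visit is 28 days after the last injection, or week 24 if that comes first.

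**The plan's own figures reproduce.** 6 cycles × 28 days = 168 days, and 168 / 7 = 24 weeks. Rest days 17 to 28 number 28 − 16 = 12.

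**Timing of the last visit.** Take day 1 as the first injection, dosing on schedule and the last injection on day 16 of cycle c. Then:
- Last injection L = 28(c − 1) + 16.
- Next cycle would start N = 28c + 1.
- Last visit V = the smaller of L + 28 and 169 (week 24 = 24 × 7 + 1).
- Week 12 = 12 × 7 + 1 = day 85.

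| c | L | N | V | Week of V, (V − 1)/7 | Week-12 reading (day 85) |
|---|---|---|---|---|---|
| 1 | 16 | 29 | 44 | 6.1 | not reached |
| 2 | 44 | 57 | 72 | 10.1 | not reached |
| 3 | 72 | 85 | 100 | 14.1 | 13 days after last injection |
| 4 | 100 | 113 | 128 | 18.1 | on treatment |
| 5 | 128 | 141 | 156 | 22.1 | on treatment |
| 6 | 156 | 169 | 169 | 24.0 | on treatment |

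For cycles 1 to 5, V − N = 15 days. (With 12 full rest days the next dose is due 13 days after the last one, and 28 − 13 = 15.) After cycle 6 the week-24 assessment comes first, so the problem does not arise.

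**Who depends on this reading alone.** The last visit reaches day 85 only if L is at least 85 − 28 = 57, which is day 1 of cycle 3. Anyone whose last injection is in cycle 1 or 2 (day 44 at the latest) has a last visit no later than day 72, 13 days short of week 12. Section 9.3.2 gives a window of 11 to 13 weeks for laboratory values; even that opens only on day 11 × 7 + 1 = 78. Weeks 4 and 8 collect no response. These patients have one scheduled reading, taken off drug.

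**Whether a rule could separate the readings.** Sections 9.2.6, 9.3.2, 9.7.2.1 and 9.7.2.5 contain none. In Appendix F, new therapy is mentioned only for relapse and progression (note 5), not for response. If a rule were added in the analysis, it would have to order two dates inside 28 days. A start date given only to the year cannot do that.

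**Size, on assumptions only.** Upward error in ORR = s × q × r, where s is the share stopping early, q the share of those who start a new regimen before the last visit, and r the share of those who turn from non-responder to counted responder because of it. The protocol gives none of the three.
- Low (10%, 10%, 10%): 0.10 × 0.10 × 0.10 = 0.1 percentage points, or 0.6 of 600 patients.
- Middle (20%, 30%, 20%): 0.20 × 0.30 × 0.20 = 1.2 points, about 7 of 600.
- High (40%, 50%, 40%): 0.40 × 0.50 × 0.40 = 8.0 points, 48 of 600.

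For scale, the 95% confidence half-width 1.96 × √(p(1 − p)/600) is 3.2 points at an ORR of 80% and 4.0 points at 50%. Here 600 is the minimum for the safety analysis; the Efficacy population may be smaller. The downward error from lost responses has no usable input and is not netted off.

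**The case against.** The strongest reply is that how to count responses after subsequent therapy is ordinarily an SAP matter, and the SAP is not shown. That holds for the counting rule by itself. It does not hold for data capture: an SAP cannot order events from a year, nor recover a pre-switch response that the schedule never asked for.

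Several other points limit the size and stand to that extent:
- A regimen begun after the last injection has less than four weeks to act, and about two if it starts near the missed cycle. A PR needs at least a 50% fall in serum M-protein (Appendix F).
- Patients who stop after cycle 4 or 5 also have an on-treatment week-12 reading, and a response seen there belongs to Kyprolis.
- The Abstract analyzes ORR at 12 and 24 weeks and section 9.7 at 24 weeks. Whether an off-schedule reading such as day 44 enters those rates is not settled.
- Responses must be confirmed and treatment must be per protocol. Either condition may remove cases, but neither is defined. If confirmation needs a second reading, patients who stop after cycle 1 or 2 have no second scheduled one; if it does not, a single post-switch reading counts.
- The study is single-arm and descriptive, ORR is secondary, and section 9.9 acknowledges bias. That lowers the stakes but does not supply the missing dates.

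**Conclusion.** The concern holds in a limited form. For early stoppers the last scheduled response reading comes 28 days after the last injection, and for those who stop after cycle 1 or 2 it is the only one. A response to a new regimen can be credited to Kyprolis, and a lost Kyprolis response can be missed. The protocol has no rule for this and does not require dates precise enough to apply one.

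A reader might infer that ORR is in fact inflated by other treatments, or that the KRd and Kd figures are distorted in a known direction. The documents do not support either. They give no rate of early stopping, switching or conversion, overall or by regimen, and the error runs both ways. The range of 0.1 to 8.0 points rests wholly on assumed inputs and describes the upward part only. A switcher who had already responded on Kyprolis is not a misattributed case and must not be counted as one.

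The 15-day gap assumes dosing on schedule with the last injection on day 16 of a cycle. The change is worth making because it is cheap and removes an avoidable ambiguity from the effectiveness endpoint. The primary safety objective is not affected.

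**What to change.** 1. Section 9.3.3: require the full start date (day, month, year) of the next anti-myeloma therapy.
2. Table 3 and section 9.3.2: for patients who stop Kyprolis early, also capture from the medical record the last routine response assessment made on or before that date.
3. Section 9.7.2.5: count toward ORR only confirmed responses first documented on or before the start of new anti-myeloma therapy, and use the last-visit reading when no new therapy has begun.

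Leave the 28-day adverse event window unchanged.

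The cost is one or two extra CRF fields and short wording changes in these places. Because assessments already follow routine practice (section 9.1) and data come from medical records (section 9.4), no visit or procedure is added. The reported ORR may be slightly lower, since some late responses would no longer count.

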### 9.3.1 Exposure Assessment

Dosage, period (start / end date), frequency of administration, drug withdrawal (Yes or No, date, reason) of Kyprolis® with lenalidomide and dexamethasone or with dexamethasone are collected in CRF.

### 9.3.2 Outcome Assessment

Adverse events (including seriousness and causal relations to drug), and other safety information (eg, overdose, lack of effectiveness, pregnancy and lactation with or without adverse event) are collected as they become available throughout the follow-up period by using CRF and applicable safety reporting form.

Laboratory values measured as a part of routine medical practice are collected in CRF for baseline, 4W (ranged; 3-5W), 8W (7-9W), 12W (11-13W), and 24W (23-25W) or at the end of follow-up.

Overall response rate: The following assessments will be required for all response categories (sCR, CR, VGPR, or PR; see definitions in [Appendix F](#)– IMWG criteria): Patients with confirmed sCR, CR, VGPR, or PR will be considered to have achieved an overall response.

### 9.3.3 Covariate Assessment

Data on the following covariates are collected in CRF.

Patient demographics and medical history: sex, birth Year/Month, height, weight, pregnancy, site name, investigator's name, medical history of disease (all cancers, and other diseases without relation with cancer within the last 2 years), cardiovascular disease, hepatic impairment, renal impairment, other concomitant diseases

Diagnostic information: information pertaining to Kyprolis® indication including date of diagnosis, international staging system (ISS) stage at study entry, site of metastasis, previous treatment for multiple myeloma or number of previous treatment and cytogenetic risk

Prior and Concomitant medication: Prior (at least 30 days) or concomitant medications including any prescription or over-the-counter preparation and targeted disease therapies or surgical treatments after start of Kyprolis® treatment. All the following variables are to be collected for concomitant medication: trade name or INN, start date (at least year), stop date or “continued” and daily dose (if applicable).

### 9.3.4 Validity and Reliability

Not applicable.

### 9.4 Data Sources

The original source of the data used in the study is patient medical records. Data are collected through CRFs, which are populated by the investigators.

Laboratory test values among variable data will be measured by each medical site with their own method.

### 9.5 Study Size

The minimum required patient number is 600 patients for the final study report. Considering follow-up loss, it is recommended 700 patients be enrolled in study.

## 9.6 Data Management

It is an observational study so that variables, which can be measured at medical sites in real-life medical practice, are selected for this study in reference to prior Kyprolis® clinical trials and advice from local medical experts.

### 9.6.1 Obtaining Data Files

Not applicable.

### 9.6.2 Linking Data Files

Not applicable.

### 9.6.3 Review and Verification of Data Quality

Data collection will be conducted by using a validated data system. Data management will be conducted under its own standard operating procedure with oversight by the Amgen Korea.

After collection of CRF, it will be checked for completeness. Missing data should be completed or commented by the investigator. Data from the CRF will be entered in the study database and validated.

Exposures, outcomes, and all other variables observed and measured by each medical site will be collected through data system. Standardized error check will be performed through data validation program. If a logical discrepancy and clear error is identified, a query form will be prepared and delivered to the institutional site investigators for clarification and correction. Site investigators and staff will be requested to check the data against medical records, and accuracy and completeness of data consistent with information in medical records will be confirmed and attested by signature of investigators. A check for duplication of patients will be done. All details of the quality checks will be described in the data management plan.

## 9.7 Data Analysis

Patient disposition, demographics and baseline characteristics will be summarized. For the safety analysis, adverse event will be presented using the number of patients, incidence proportion and number of events. For the effectiveness analysis, overall response rate at 24 weeks after drug administration will be analysed.

### 9.7.1 Planned Analyses

Analysis of interim data will be performed at the timing of MFDS periodic interim report (every 6 months for the first 2 years and annually thereafter until re-examination). The final analysis will be conducted at the timing of MFDS re-examination (after 6 years). If

patient enrollment reaches 700 (considering drop-out), the enrollment will stop and the final analysis will be conducted after 6 years.

#### **9.7.1.1 Interim Analysis/Analyses**

There will be interim analyses to support safety reporting and assessments of effectiveness endpoints.

Under regulatory requirement, periodical analyses will be conducted in a timeline aligned to MFDS periodic interim report (every 6 months for the first 2 years and annually thereafter until re-examination). The interim result will be reported as a part of MFDS periodic interim report.

#### **9.7.1.2 Final Analysis**

The final analysis will be conducted for the re-examination report after all the study data are collected and cleaned.

Patient disposition, demographics and baseline characteristics will be summarized. For the safety analysis, adverse event will be presented using the number of patients, incidence proportion and number of events. For the effectiveness analysis, overall response rate after drug administration will be analysed.

### **9.7.2 Planned Method of Analysis**

#### **9.7.2.1 Analysis Populations**

The data will be analyzed using 3 patient populations: CRF-collected population, Safety population and Efficacy population. Reasons for withdrawal will be described for the withdrawn patients.

- CRF-collected population: All patients from whom CRFs have been collected
- Safety population: All patients who have received at least one dose of study product and on whom a follow-up (including telephone visit) has been conducted.
- Efficacy population: All patients who have been included in the Safety population, who also have received study product per protocol, and on whom any post-baseline efficacy evaluation has been done.

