## **8. Research Question and Objectives**

To obtain the safety information and effectiveness of the product in the real-life use of Kyprolis® in Korea.

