### **8.2 Secondary**

The secondary objective of this study is to investigate effectiveness of Kyprolis® (Overall Response Rate).

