#### **9.7.2.3 Missing or Incomplete Data and Lost to Follow-up**

No imputation is to be performed.

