#### 9.7.2.4 Descriptive Analysis

##### 9.7.2.4.1 Description of Study Enrollment

All enrolled patients will be summarized in the tree of patient disposition, as described below:

enrollment	XXXX cases	(a%)
	Exclude from safety	XX cases
	Reason)	
	Non received an IP	XX cases
Safety analysis	XXXX cases	(b%)
	Exclude form effectiveness	X cases
	Reason)	
	No effectiveness assessment	X cases
Effectiveness analysis	XXXX cases	(c%)

Percentage of a%, b% and c% (corresponding to enrollment) will be calculated.

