##### 9.7.2.5 Analysis of the Primary, Secondary and Exploratory Endpoint(s)

Analysis for specified endpoints will be conducted as follows:

- Safety endpoint:  
Number of patients, subject incidence\_with adverse events, adverse drug reactions and serious adverse events during the observational period will be calculated and summarized (see [Section 11.1](#) the definition of adverse event, serious adverse event, and other safety findings to be collected).
- Effectiveness endpoint:  
Overall response rate for disease assessment - Patients with confirmed sCR, CR, VGPR, or PR will be considered to have achieved an overall response.

Approved

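### The response rate is confined to patients assessed and treated under an undefined per-protocol condition, so it is likely overstated as a real-life rate

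*Protocol*

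**What the plan says.** The research question in Section 8 of the protocol is "To obtain the safety information and effectiveness of the product in the real-life use of Kyprolis® in Korea". ORR is the only effectiveness endpoint and is secondary (Section 8.2). Section 9.7.2.5 defines the numerator: "Patients with confirmed sCR, CR, VGPR, or PR will be considered to have achieved an overall response". It states no denominator.

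The denominator has to come from Section 9.7.2.1. The Safety population is "All patients who have received at least one dose of study product and on whom a follow-up (including telephone visit) has been conducted". The Efficacy population is the part of that set "who also have received study product per protocol, and on whom any post-baseline efficacy evaluation has been done".

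Other sections bear on it:

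- Section 9.7.2.3 on missing data: "No imputation is to be performed".
- Section 9.7.2.6.3 plans no sensitivity analysis.
- The disposition tree in Section 9.7.2.4.1 gives one reason for leaving the effectiveness analysis: "No effectiveness assessment".
- Section 9.7.2.6.1 plans subgroup results by regimen and by dose, for effectiveness as well as for adverse events.
- Section 9.1 has response captured at weeks 12 and 24 as routine practice allows.
- Section 9.2.6 ends follow-up at death, loss to follow-up, "28 days from the last injection of Kyprolis® or 24 weeks after initial prescription of Kyprolis®, whichever occurs first".
- Table 3 marks a tumor response assessment at the last visit. Its footnote 5 allows a clinical judgement when a deteriorating patient cannot have imaging.

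**The concern.** Membership of the Efficacy population depends on two things that happen after treatment starts.

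The first is having a response evaluation. A patient who dies or is lost before any evaluation drops out of the denominator. Patients lost to early death or deterioration can be expected to respond less often than those who stay, so removing them tends to raise ORR. A larger sample does not reduce this.

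The second is having received product per protocol. The study observes prescribing and assigns nothing, and the phrase is not explained. Two analysts could apply it differently and reach different denominators from the same data.

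The resulting ORR goes into the periodic interim reports and the re-examination report to the regulator (Sections 9.7.1 and 9.7.1.2). It would be read as effectiveness in routine use while leaving out some of the patients in routine use.

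**Working it through.** **1. What the protocol supplies.** It gives no expected ORR and no expected share of unassessed patients. Its only related figure is enrolment of 700 to secure 600 for the safety analysis (Sections 9.1 and 9.5). The implied allowance is 1 − 600/700 = 14.3%. No loss rate is stated, so this is only back-solved, and it concerns the safety analysis, not response assessment. It is not used below.

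**2. Who leaves the denominator.** Setting Sections 9.2.6 and 9.7.2.1 beside Table 3:

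- Early death or loss to follow-up before any assessment: excluded, because no last visit can supply one.
- No assessment done in routine practice: excluded.
- Stopping before week 12: not automatically excluded, because Table 3 schedules a response assessment 28 days after the last injection.
- Documented progression: kept and counted as a non-responder, because progressive disease is a response category in Appendix F.
- One assessment only: kept, because any post-baseline evaluation is enough.
- Treated but never contacted again: excluded already at the Safety population.

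**3. From the assessed rate to the all-treated rate.** Let p_A be ORR among assessed patients and f the unassessed share. If none of the unassessed responded, ORR over all treated = p_A(1 − f). If all of them responded, it is p_A(1 − f) + f. With p_A = 75% (assumed):

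| f (assumed) | None responded | Gap, points | All responded |
|---|---|---|---|
| 5% | 0.75 × 0.95 = 71.3% | 3.75 | 76.3% |
| 10% | 0.75 × 0.90 = 67.5% | 7.5 | 77.5% |
| 20% | 0.75 × 0.80 = 60.0% | 15.0 | 80.0% |

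For scale, the 95% half-width at N = 600 is 1.96 × √(0.75 × 0.25/600) = 3.5 points. The 5% case already matches it if none of the unassessed responded.

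**4. How far the direction is fixed.** Let p be ORR in all treated patients and q the response rate of excluded patients relative to p. The reported rate is (p − q·p·f)/(1 − f). With p = 70% (assumed):

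| q | f = 10% | f = 20% |
|---|---|---|
| 0 | 77.8% (+7.8) | 87.5% (+17.5) |
| 0.5 | 73.9% (+3.9) | 78.8% (+8.8) |
| 1 | 70.0% (0) | 70.0% (0) |
| 1.2 | 68.4% (−1.6) | 66.5% (−3.5) |

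The rate is overstated whenever excluded patients respond less often than the whole. That is the expected case for early death and deterioration. It is not established for patients excluded over how they received the product.

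**5. The per-protocol condition.** Tables 1 and 2 are the only dosing schedules in the document. Regimens outside the approved label are already excluded at entry (Section 9.2.3.2). The phrase could mean adherence to those schedules or simply receipt of an eligible regimen. The first reading fits badly with Section 9.7.2.6.1, which lists dose separately from regimen as a subgroup for effectiveness. The second adds little to the entry criteria. The text does not choose between them.

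**The case against.** The strongest case against is that the exclusion may be small. Table 3 gives early stoppers a scheduled assessment, footnote 5 provides a fallback, progressors count as non-responders, and a single evaluation is enough. This stands, and it narrows the affected group mainly to early deaths, losses to follow-up and patients not assessed in practice. A reader might infer that everyone who progresses or stops for toxicity drops out; Table 3 does not support that.

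A reader might also infer that the bias must run upward. Section 9.2.6 gives transfer to another clinic as its example of loss, and such patients may have responded. For dosing-based exclusions the sign is open.

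Nor can the median progression-free survival figures in Section 7.1 size the problem. They count progression or death, and documented progressors stay in the denominator.

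It is also tempting to say that the disposition tree sets a second, conflicting denominator. It is a table shell with sample reasons: its safety step shows only non-receipt of product, although the Safety population also requires a follow-up contact. The missing per-protocol line shows that the condition is not carried through, not that a rival denominator was intended. The rule against imputation likewise removes nobody; the population definition does that.

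Finally, the study is descriptive, Section 9.9 admits missing data and selection bias, the tree will show how many patients were excluded, and an analysis plan not seen here may add a table. A reader could rebuild part of the all-treated rate from the tree. That would not recover responders removed under the per-protocol condition, or treated patients with no follow-up contact. What an analysis plan might add does not cure a population that the protocol itself fixes in these terms.

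**Conclusion.** The point holds in a limited form. The only population defined for effectiveness leaves out patients without a response evaluation and applies an undefined treatment condition, and no all-treated ORR or sensitivity analysis stands beside it. The reported ORR is therefore likely, though not certain, to overstate the real-life rate.

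On an assumed 75% among assessed patients, the overstatement is at most 3.75, 7.5 or 15 points for 5%, 10% or 20% unassessed. Both the 75% and the shares are assumptions, and each limit is reached only if no unassessed patient responded. The direction of any effect of the per-protocol condition is not determined.

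It should be fixed, but it is not critical: ORR is a secondary descriptive endpoint in a safety surveillance study with no hypothesis to test.

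**What to change.** - Make all patients with at least one dose the main ORR denominator, and count those without an evaluable post-baseline response as non-responders.
- Delete the per-protocol receipt condition from the Efficacy population. Alternatively, define it as receipt of an eligible KRd or Kd regimen, and reconcile it with the disposition tree (Section 9.7.2.4.1) and the planned effectiveness analysis by dose (Section 9.7.2.6.1).
- Keep the ORR among response-evaluable patients as a labelled supportive table.
- Report how many patients were unassessed and why, separating death, loss to follow-up and no assessment done.

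The cost is protocol wording, one extra table and a headline ORR that will be lower if any treated patient is unassessed. No new data are needed.
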